16.4.3. Treatment State

Within each treatment study phase (i.e. Maintenance, and Extension—based on assignment of study phase described in Section 16.4.1), only those assessments which occur within the ranges shown below will be considered ‘on-treatment’ for the given phase. Note “on-treatment” criteria will not be implemented for adverse event summaries.

Table 7 Treatment State within Study Phases

Study Phase ^a	Treatment State	Date Range
Screen	Pre-treatment	All assessments/events within Phase
Maintenance	On-treatment	Q2M Arm: Date ≤ max (Date of Last Injection Dose + 67, Date of Last Oral Dose + 1)
		BIK Arm: Date ≤ Maintenance ART Stop Date + 1
	Post-treatment	Q2M Arm: Date > max (Date of Last Injection Dose + 67, Date of Last Oral Dose + 1)
		BIK Arm: Date > Maintenance ART Stop Date + 1
Extension	On-treatment	Date ≤ max (Date of Last IP Injection Dose + 67, Date of Last Oral Dose + 1)
	Post-treatment	Date > max (Date of Last IP Injection Dose + 67, Date of Last Oral Dose + 1)
Long-Term Follow-up	On-treatment	Date ≤ min (LTFU ART start date, max (Date of Last IP Injection Date + 67, Date of Last Oral Dose + 1))
	Post-treatment	Date > min (LTFU ART start date, max (Date of Last IP Injection Date + 67, Date of Last Oral Dose + 1))
Note: 
 Treatment State is determined after data has been assigned to the study Phases as defined in Section 16.4.1 		

- The upper bound with last IP injection / last oral dose /Maintenance ART Stop Date should only be applied to participants who permanently discontinue from study treatment
- Date = Assessment/Start Date.
- Last oral dose may be CAB/RPV or SOC ART Oral Bridging where CAB/RPV is not available due to COVID-19.

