16.9. Appendix 9: Snapshot Algorithm Details

Detailed Algorithm Steps

- Consider an analysis visit window for Month X as defined in Section [16.3.1](#)
- The HIV-1 RNA threshold of 50, 200 copies/mL will be analysed, respectively, in this study.
- The COVID-19 pandemic presents significant logistical challenges for many clinical sites around the world, with variable restrictions being placed on site resources and operations, and on an individual participant's ability to attend clinic visits. The snapshot algorithm is modified to allow for the presentation of full scope of COVID-19 relatedness. The analysis window 'Week 48' and HIV-1 RNA threshold of '50 c/mL' are used for the purpose of illustration. A participant's Snapshot response and reason at Week 48 are categorized as below.
 - HIV-1 RNA < 50 c/mL
 - HIV-1 RNA ≥ 50 c/mL
 - Data in window not below threshold
 - Non-COVID-19 related
 - Discontinued for lack of efficacy
 - Discontinued for other reason while not below threshold
 - Change in background therapy*
 - COVID-19 related
 - Discontinued for lack of efficacy
 - Discontinued for other reason while not below threshold
 - Change in background therapy*
 - No Virologic Data at Week 48 Window
 - Non-COVID-19 related
 - Discontinued study due to AE or death
 - Discontinued study for other reasons
 - Not evaluated or discontinued due to confirmed pregnancy**
 - On study but missing data in window
 - COVID-19 related
 - Discontinued study due to AE or death
 - Discontinued study for other reason
 - On study but missing data in window

- Note: since permanent changes in ART are not permitted in this protocol, all such participants who permanently change ART will be considered 'HIV-1 RNA \geq 50 c/mL' if the change is made prior to an analysis timepoint. Participants with protocol permitted oral bridging treatment, CAB+RPV or SOC (during COVID-19 pandemic due to the unavailability of the CAB/RPV IM injections and oral CAB+RPV), or a temporary change in ART by mistake prior to an analysis timepoint (e.g. participant took the ART different from study treatment during oral lead-in by mistake for a short period of time and then went back to the study treatment) will not be considered 'HIV-1 RNA \geq 50 c/mL' due to 'change in ART'.
- The steps in determining response and reasons are indicated in Table below, in the order stated.

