5.2.2.3 Non-safety and Non-COVID-19 related reasons (e.g. Lack of efficacy, protocol deviation, withdrew consent, loss to follow-up, study closed/terminated, investigator discretion etc, as recorded in eCRF Conclusion Form)		

 ◦ Last on-treatment VL <50 c/mL OR no on-treatment VL available during study 		

 • Withdrew not due to pregnancy 	No virologic Data at Week 48 Window	Disc for other reasons (Non-COVID-19 related)

 • Withdrew due to pregnancy 	No virologic Data at Week 48 Window	Not evaluated or discontinued due to confirmed pregnancy(Non-COVID-19 related)

 ◦ Last on-treatment VL ≥ 50 c/mL AND withdrawal due to Lack of efficacy 	HIV-1 RNA ≥ 50	Disc. for lack of efficacy (Non-COVID-19 related)

 ◦ Last on-treatment VL ≥ 50 c/mL AND withdrawal due to all other non-safety related reasons 	HIV-1 RNA ≥ 50	Disc. for other reason while not below 50 (Non-COVID-19 related)
5.2.2.4 Non-safety and COVID-19 related reasons (e.g. protocol deviation, withdrew consent, loss to follow-up, study closed/terminated, investigator discretion etc., as recorded in eCRF Conclusion Form)		

 • Last on-treatment VL <50 c/mL OR no on-treatment VL available during study 	No virologic Data at Week 48 Window	Disc for other reasons (COVID-19 related)

 • Last on-treatment VL ≥ 50 c/mL AND withdrawal due to Lack of efficacy 	HIV-1 RNA ≥ 50	Disc. for lack of efficacy (COVID-19 related)

 • Last on-treatment VL ≥ 50 c/mL AND withdrawal due to all other non-safety related reasons 	HIV-1 RNA ≥ 50	Disc. for other reason while not below 50 (COVID-19 related)

 • Excluding permitted change in background therapy where change or decision to change is made prior to/on the first on-treatment viral result 		

Examples from FDA guidanceData in Window

Virologic outcome should be determined by the last available measurement while the patient is on treatment and continued on trial within the time window:

- HIV-RNA = 580 copies/mL at Day 336, HIV-RNA below 50 copies/mL on Day 350. This should be categorized as HIV-RNA below 50 copies/mL.

No Data in Window

Discontinued study due to Adverse Event or Death:

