- Any patient who discontinues because of an AE or death before the window should be classified as *Discontinued due to AE or Death* (as appropriate), regardless of the HIV-RNA result, even if the HIV-RNA is below 50 copies/mL at the time of discontinuation.
- However, if a patient has an HIV-RNA value in the time window and also discontinues in the time window, the viral load data should be used to classify the patient's response. This is the Virology First hierarchy:
 - HIV-RNA below 50 copies/mL at Day 336 and discontinues because of AE or even dies on Day 360 — this person is categorized as having HIV-RNA below 50 copies/mL.
 - HIV-RNA is 552 copies/mL on Day 336 and the patient discontinues on Day 360, the patient is categorized as having HIV-RNA greater than or equal to 50 copies/mL.

Discontinued for Other Reasons:

- Only patients who have achieved virologic suppression can be counted as *Discontinued for Other Reasons*.
- If a patient discontinues the study before the time window because of *lack of efficacy* then the patient should be included in the HIV-RNA greater than or equal to 50 row and not in the Discontinued for Other Reasons row.
- If a patient discontinues because of *subject withdrew consent* and his or her HIV-1 RNA result at the time of discontinuation was equal to or above 50 copies/mL, then he or she should be categorized as HIV-RNA greater than or equal to 50 and NOT as Discontinued for Other Reasons.
- If a patient discontinued because of *Lost to Follow-Up* and the last HIV-RNA result was 49 copies/mL, then the patient can be categorized as Discontinued for Other Reasons.
- If patients changed background treatment — *not permitted by protocol*— they should be considered an efficacy failure and captured in the HIV-RNA greater than or equal to 50 copies/mL row.

On study but missing data in window:

- If there are no data during Days 294 to 377, but there is an HIV-RNA below 50 copies/mL on Day 380, this patient should be considered *On Study but Missing Data in Window*.

- If there are no data during Days 294 to 377, but there is an HIV-RNA equal to or above 50 copies/mL on Day 280, this patient also should be classified as *On Study but Missing Data in Window*.

Not evaluated due to confirmed pregnancy:

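### Snapshot steps 5.2.2.3 and 5.2.2.4 put some lack-of-efficacy withdrawals in the no-data category, while the FDA text in the same appendix counts them as HIV-1 RNA ≥50 c/mL

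*SAP*

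**What the plan says.** The primary endpoint is the proportion with HIV-1 RNA ≥50 c/mL by the FDA Snapshot algorithm (SAP 2.2 and 7.1.1). Section 7.1.5.1 refers to Appendix 9 for the details.

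Appendix 9 makes its step table the operative text: "The steps in determining response and reasons are indicated in Table below, in the order stated". Step 5.2.2 handles participants who withdraw before or during the window and have no on-treatment viral load in it. The relevant step opens with "5.2.2.3 Non-safety and Non-COVID-19 related reasons (e.g. Lack of efficacy, protocol deviation, withdrew consent", so lack of efficacy is inside it. Its branches are:

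- "Last on-treatment VL <50 c/mL OR no on-treatment VL available during study": no virologic data, with reason "Disc for other reasons (Non-COVID-19 related" unless the withdrawal was due to pregnancy.
- Last on-treatment viral load ≥50 c/mL "AND withdrawal due to Lack of efficacy": HIV-1 RNA ≥50.
- Last on-treatment viral load ≥50 c/mL and any other non-safety reason: HIV-1 RNA ≥50.

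Step 5.2.2.4 repeats this for COVID-19-related withdrawals. Its header does not list lack of efficacy, but its ≥50 branches do.

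Further on in the appendix, the FDA guidance examples deal with a participant who stops for lack of efficacy ahead of the window, and the instruction reads: "then the patient should be included in the HIV-RNA greater than or equal to 50 row and not in the Discontinued for Other Reasons". No viral-load condition is attached.

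**The concern.** A participant withdrawn for lack of efficacy before the window whose last on-treatment value is below 50 c/mL, or who has none, falls in a different row depending on which part of Appendix 9 is read. One row is in the primary numerator and the other is not. In the step table the lack-of-efficacy branch has no effect on response. A last value ≥50 already gives ≥50 for every non-safety reason, so naming lack of efficacy changes only the label.

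The primary numerator is therefore at stake in a trial where few events can be expected, and the SAP tests superiority after non-inferiority (5.5.1).

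**Working it through.** **Tracing the rule.** Take a withdrawal for lack of efficacy before the window, with no permanent ART change (which condition 1 would already count as ≥50) and no on-treatment value in the window.

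| Last on-treatment viral load | Step table | FDA text in Appendix 9 |
|---|---|---|
| ≥50 c/mL | ≥50 | ≥50 |
| <50 c/mL | No virologic data, other reasons | ≥50 |
| None | No virologic data, other reasons | ≥50 |

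The conflict is confined to the last two rows. The FDA text speaks only of stopping before the window, so for withdrawal during the window there is no explicit conflict.

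**Other parts of the SAP.**
- Appendix 9's outline of categories lists discontinuation for lack of efficacy under ≥50 without qualification. The neighbouring other-reason category does carry a not-below-threshold condition. This agrees with the FDA text.
- Section 16.6.3 and Appendix 10 count withdrawal for lack of efficacy as an event in both the TRDF and ERDF Kaplan-Meier analyses, whatever the viral load. The same participant is then an efficacy failure in Table 2.26 and an other-reasons discontinuation behind Table 2.1.
- Sections 7.1.4 and 7.1.5.1 require RNA ≥50 at discontinuation for a non-AE withdrawal to count. They agree with the step table, but do not mention lack of efficacy.

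**Size.** The SAP states no event rates or power, so there is no figure of its own to reproduce. Inputs:
- About 654 randomized 2:1 (2.3), less 11 excluded from mITT-E (2.1), leaves 643.
- A 2:1 split of 643 gives 429 and 214. This split is an assumption.
- The margin is 4% (2.4).

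Shift per reclassified participant: 1/429 = 0.23 points upward for Q2M; 1/214 = 0.47 points downward for BIK.

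For the confidence limit I used the SAP's CMH estimate and Sato variance (7.1.5.1) collapsed to one stratum, where x and y are the Q2M and BIK event counts:

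d = x/n − y/m; W = nm/N; P = [n²y − m²x + nm(m − n)/2]/N²; Q = [x(m − y) + y(n − x)]/(2N); var = (dP + Q)/W²; upper limit = d + 1.96√var.

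Here n = 429, m = 214, N = 643 and W = 142.78. With an assumed 4 versus 2 events (about 1% per arm), d ≈ 0.00%, P = −23.42 and Q = 1.320, so √var = 0.805% and the upper limit is 1.58%.

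| Added to 4 versus 2 | d | Upper 95% limit |
|---|---|---|
| One Q2M case | 0.23% | 1.87% |
| Two Q2M cases | 0.46% | 2.17% |
| One BIK case | −0.47% | 1.35% |
| Eight Q2M cases | 1.86% | 3.89% |
| Nine Q2M cases | 2.10% | 4.17% |

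Q2M-only cases needed to lose the margin at other assumed rates (Q2M/BIK): 10 at 0.5%/0.5%, 6 at 2%/2%, 4 at 2%/1%.

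Superiority can be more sensitive. At an assumed 1 versus 5 events the upper limit is −0.03%. With one Q2M reclassification (2 versus 5) it is +0.25%, and superiority is lost.

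**The case against.** The strongest reply is that a programmer faces no ambiguity. Appendix 9 says the table decides, the table agrees with 7.1.4 and 7.1.5.1, and the outlier is one bullet among generic guidance examples that use Days 294 to 377 rather than this trial's windows (16.3.2.6). That stands as to which text governs. It does not remove the departure: the endpoint is defined by the FDA algorithm, the bullet is the SAP's own statement of that algorithm, and nothing says the difference is intended.

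The group is also likely to be small. It needs withdrawal for lack of efficacy, a last value below 50 or none, no value in the window, and no ART change caught by condition 1. Section 16.15.10 records fewer than 5 CVFs in total at Month 6. These participants also remain visible in the Kaplan-Meier analyses, the cumulative CVF table and the listings, and they are not counted as <50 c/mL in the key secondary endpoint. All of this stands and limits the consequence.

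A reader might infer two stronger things:

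- **That true virologic failures are removed.** The documents do not show this. Those affected were below 50 c/mL at their last on-treatment measurement or had none. They are failures only under the quoted convention.
- **That the rule favours Q2M.** On-treatment status in Q2M runs to "Date ≤ max (Date of Last Injection Dose + 67, Date of Last Oral Dose + 1") but in BIK only to one day after the stop date (16.4.3). The longer period gives more chance to record a late value below 50, but it equally keeps later values ≥50 countable. For Q2M participants not continuing into the Extension, it is also cut off when follow-up ART starts (16.4.1.2). The SAP does not show which effect dominates.

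**Conclusion.** The point holds as an inconsistency in the primary-endpoint algorithm. For a lack-of-efficacy withdrawal before the window with no in-window value, the operative steps depart from the FDA Snapshot text that the same appendix reproduces, and from the way the ERDF and TRDF analyses treat the same participant.

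The number affected is unknown and the direction depends on the arm in which the cases fall. The sizes rest on an assumed 429/214 split, assumed event rates of 0.5% to 2% and a single stratum. On that basis a reversal of non-inferiority is unlikely, whereas a single case could decide a borderline superiority test. The correction is warranted because the rule for the primary numerator should have one answer, not because the main conclusion is in evident danger.

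**What to change.** In steps 5.2.2.3 and 5.2.2.4:

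1. Add a first branch: withdrawal for lack of efficacy before the window, with no on-treatment viral load in the window, is HIV-1 RNA ≥50 (discontinued for lack of efficacy), whatever the last viral load.
2. Restrict the below-50-or-none branch to the other non-safety reasons.
3. State explicitly how withdrawal for lack of efficacy during the window without a viral load is classified, since the quoted FDA text does not cover it.
4. Align 7.1.4, 7.1.5.1 and 7.2.5.1 with the result.

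The Month 6 analysis was done before the first SAP amendment, and the list of changes in Section 1 shows none to Appendix 9, so it will have used the current rule. The change should therefore be documented with its reason, and the primary result under the current rule reported as a sensitivity analysis, with the number of participants reclassified in each arm.

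The cost is a few lines of SAP text and Snapshot code, one additional table and the justification for a change after the interim. No further data are needed.

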16.10. Appendix 10: Variables Defined for Time to Event Analysis

Programming Instructions for the Kaplan-Meier analysis of treatment-related discontinuation equals failure (TRDF)		
Condition	Censor Status	Event Description/AVAL
1. Participant met CVF event criteria during the Maintenance Phase (based on derived CVF)	CNSR=0	EVNTDESC=CVF AVAL=Study Day of SVF* *immediately preceding CVF
2. Participant with Maintenance Phase withdrawal due to ' Lack of Efficacy ', ' Treatment Related AE ', ' Intolerability due to Injection ', or ' Protocol Defined Safety Stopping Criteria ' during Maintenance Phase Note: primary reason and/or standardized subreason for discontinuation based on Maintenance Conclusion form in the eCRF. ' Protocol Defined Safety Stopping Criteria ' includes GSK defined liver chemistry stopping criteria, renal toxicity criteria and QTc withdrawal criteria. Treatment Related AE' is defined as participants who have primary reason for withdrawal =AE and who have at least one AE considered drug related and leading to withdrawal/permanent discontinuation of investigational product.	CNSR=0	EVNTDESC= terms in italic , respectively. For Q2M arm: AVAL= min [Study Day of Maintenance Phase Discontinuation, Study day of Starting LTFU HAART if applicable, max(Study Day of Last Maintenance Q2M IM Dose + 67, Study Day of Last Maintenance Oral Dose + 1)] For BIK arm: AVAL= min [Study Day of Maintenance Phase Discontinuation, Study Day of Maintenance IP Stop Date + 1] Note: 
 • Last Q2M IM / last oral dose/ Maintenance IP Stop Date only applies to subjects who permanently discontinue from study treatment. • Date of Maintenance Phase discontinuation is from the Maintenance Phase Conclusion form in the eCRF.
If none of the above conditions met		
3. Participant with Maintenance Phase withdrawal due to other reasons	CNSR=1	EVNTDESC='Censored due to Study Discontinuation for Other Reasons' AVAL will be defined as the same as above 2
4. Participant who did not have premature withdrawal from the Maintenance Phase	CNSR=1	EVNTDESC='Censored due to data cutoff for analysis'

Programming Instructions for the Kaplan-Meier analysis of treatment-related discontinuation equals failure (TRDF)		
Condition	Censor Status	Event Description/AVAL
		
AVAL = Study Day of last on-treatment date during the maintenance phase, which is defined as follows:
 
For Q2M arm: min [Study Day of Month 13(D2I)/14(OLI) Visit, Study Day of Starting LTFU HAART, Study Day of Last Contact Date at time of analysis, max(Study Day of Last Maintenance Q2M IM Dose + 67, Study Day of Last Maintenance oral dose + 1)]
 
For BIK arm: min [Study Day of Month 13 Visit, Day of Last Contact at time of analysis, Study Day of Maintenance IP stop Date + 1]
 
Note:
 
 Last Q2M IM / last oral dose/ Maintenance IP Stop Date only applies to subjects who permanently discontinue from study treatment

*Last oral dose may be CAB/RPV or SOC ART Oral Bridging where CAB/RPV is not available due to COVID-19 impact.

Note that last injection and last oral dose mentioned above are only applied to participants who permanently discontinued from the study treatment.

The similar approach will be used to derive for Kaplan-Meier analysis of efficacy-related discontinuation equals failure (ERDF), except that the reason of withdrawal in Condition 2 will be restricted to 'Lack of Efficacy'.

16.11. Appendix 11: Identification of Adverse Events of Special Interest (AESI)

The adverse events of special interest are identified based on MedDRA coded values and/or AE data available in the study database. The PT terms and codes below are from MedDRA 24.1. SMQs use narrow terms unless otherwise specified. In case there is a change to the version of MedDRA at time of reporting, the coded values based on the MedDRA version at the time of reporting will be used. Additional events may be added based on the blinded review of AE data collected on study prior to the database freeze.

16.11.1. Hepatic Safety Profile

Hepatic failure, fibrosis and cirrhosis and other liver damage-related conditions (SMQ)

PT	PT Code
Acquired hepatocerebral degeneration	10080860
Acute hepatic failure	10000804
Acute on chronic liver failure	10077305
Acute yellow liver atrophy	10070815
Ascites	10003445
Asterixis	10003547
Bacterascites	10068547
Biliary cirrhosis	10004659
Biliary fibrosis	10004664
Cardiohepatic syndrome	10082480
Cholestatic liver injury	10067969
Chronic hepatic failure	10057573
Coma hepatic	10010075
Cryptogenic cirrhosis	10063075
Diabetic hepatopathy	10071265
Drug-induced liver injury	10072268
Duodenal varices	10051010
Flood syndrome	10084797
Gallbladder varices	10072319
Gastric variceal injection	10076237
Gastric variceal ligation	10076238
Gastric varices	10051012
Gastric varices haemorrhage	10057572
Gastroesophageal variceal haemorrhage prophylaxis	10066597
Hepatectomy	10061997
Hepatic atrophy	10019637
Hepatic calcification	10065274
Hepatic cirrhosis	10019641

PT	PT Code
Hepatic encephalopathy	10019660
Hepatic encephalopathy prophylaxis	10066599
Hepatic failure	10019663
Hepatic fibrosis	10019668
Hepatic hydrothorax	10067365
Hepatic infiltration eosinophilic	10064668
Hepatic lesion	10061998
Hepatic necrosis	10019692
Hepatic steato-fibrosis	10077215
Hepatic steatosis	10019708
Hepatitis fulminant	10019772
Hepatobiliary disease	10062000
Hepatocellular foamy cell syndrome	10053244
Hepatocellular injury	10019837
Hepatopulmonary syndrome	10052274
Hepatorenal failure	10019845
Hepatorenal syndrome	10019846
Hepatotoxicity	10019851
Immune-mediated cholangitis	10083406
Immune-mediated hepatic disorder	10083521
Intestinal varices	10071502
Intestinal varices haemorrhage	10078058
Liver dialysis	10076640
Liver disorder	10024670
Liver injury	10067125
Liver operation	10062040
Liver transplant	10024714
Lupoid hepatic cirrhosis	10025129
Mixed liver injury	10066758
Nodular regenerative hyperplasia	10051081
Nonalcoholic fatty liver disease	10082249
Non-alcoholic steatohepatitis	10053219
Non-cirrhotic portal hypertension	10077259
Oedema due to hepatic disease	10049631
Oesophageal varices haemorrhage	10030210
Peripancreatic varices	10073215
Portal fibrosis	10074726
Portal hypertension	10036200
Portal hypertensive colopathy	10079446

PT	PT Code
Portal hypertensive enteropathy	10068923
Portal hypertensive gastropathy	10050897
Portal vein cavernous transformation	10073979
Portal vein dilatation	10073209
Portopulmonary hypertension	10067281
Primary biliary cholangitis	10080429
Regenerative siderotic hepatic nodule	10080679
Renal and liver transplant	10052279
Retrograde portal vein flow	10067338
Reye's syndrome	10039012
Reynold's syndrome	10070953
Splenic varices	10067823
Splenic varices haemorrhage	10068662
Steatohepatitis	10076331
Subacute hepatic failure	10056956
Sugiura procedure	10083010
Varices oesophageal	10056091
Varicose veins of abdominal wall	10072284
White nipple sign	10078438
Hepatic cytolysis	10049199
Spontaneous bacterial peritonitis	10061135

Hepatitis, non-infectious (SMQ)

PT	PT Code
Acute graft versus host disease in liver	10066263
Allergic hepatitis	10071198
Alloimmune hepatitis	10080576
Autoimmune hepatitis	10003827
Chronic graft versus host disease in liver	10072160
Chronic hepatitis	10008909
Graft versus host disease in liver	10064676
Hepatitis	10019717
Hepatitis acute	10019727
Hepatitis cholestatic	10019754
Hepatitis chronic active	10019755
Hepatitis chronic persistent	10019759
Hepatitis fulminant	10019772
Hepatitis toxic	10019795

PT	PT Code
Immune-mediated hepatitis	10078962
Ischaemic hepatitis	10023025
Lupus hepatitis	10067737
Non-alcoholic steatohepatitis	10053219
Radiation hepatitis	10051015
Steatohepatitis	10076331
Hepatic cytolysis	10049199

